4. ***WIC provider counseling:*** There is evidence that WIC counseling is trusted,⁵⁴⁻⁵⁶ yet WIC nutritionists find it difficult to adequately address gestational weight gain at routine visits.²⁷ Our treatment is designed to encourage a patient-centered counseling approach (e.g., responsive to individual preference, needs, and values) while at the same time overcome barriers, including: time constraints (by supplying progress reports and brief recommendations); failure to follow-up in-between visits (which will be largely automated); and fear of causing offense (which will be resolved through role play and group discussion). There is strong support for integrating our intervention into WIC care (see letter from initial IRB submission). Participants will have monthly to bimonthly study-related phone calls from a WIC nutritionist (aka, WIC Champion, [name]) to set goals, overcome challenges, and give participants new information about diet and activity while they are in the program. These calls will last 15- 30 minutes and will be audiotaped (for training and feedback). Additionally, if participants agree, they will also receive in-person support at their regularly scheduled WIC visits every 2-3 months. While WIC is conducting visits virtually, we will not be using this approach. To inform counseling, we will supply the WIC champion with coaching protocols for new goal assignment calls that will be adapted from our prior pregnancy and postpartum weight control trials during study start-up. The goal assignment calls will take place in 8 week intervals for each participant. Additionally, the WIC champion will be notified when a participant in this group is -0.3kg from her weekly maximum IOM recommended weight gain targets or above⁵⁷ and the WIC champion will be asked to call these participants within 48 hours using adapted problem solving call scripts to enhance motivation for behavior change, deliver in-depth skills training, engage in problem solving, and provide social support. We will set a call ceiling of 1, 15-30 minute call monthly so to not overburden providers, but instead harness a potentially

important opportunity for impacting behavior change and ensuring safety.

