- i. **Primary outcome.** *The primary outcome is the proportion of women with excessive gestational weight gain*, defined as the proportion of mothers exceeding weekly Institute of Medicine (IOM) weight gain targets (>0.32 kg/week for BMI 25-29.9 kg/m²; >0.27 kg/week for BMI ≥ 30 kg/m²) over the study period (from enrollment to end of pregnancy).⁵⁷ Total gestational weight gain will be calculated as the difference between weight in kilograms measured at 36-38 weeks' gestation (end of pregnancy) and weight at the baseline visit (in the first trimester or early second trimester of pregnancy). Weight in clinical gowns, without shoes, will be recorded in duplicate by trained staff using high-quality, calibrated SECA digital scales. We will also use BodyTrace scales for patients seeking a remote option (and/or during restrictions to in-person visits during the Covid-19 pandemic) that will be sent to the participant after completion of the combined CS/EN call. In the rare case that a mother delivers her infant before 36-38 weeks' gestation, we will abstract her last prenatal weight from her obstetric chart and call her within 2 weeks of delivery to administer our follow-up

survey. We expect to abstract weights in <10% of mothers based on previous experiences with the target population. Height will be measured to the nearest 0.1 cm using a calibrated stadiometer at participants' in-person baseline assessments or via self-report via phone.

ii. **Secondary and patient-centered outcomes.**

1. ***Dietary intake*** will be measured using the Automated Self-Administered 24-hour (ASA24) dietary assessment tool, a web application developed by NCI.⁶⁹ We will collect one 24-hour dietary recall during combined CS/EN visit or call and during the end of pregnancy visit. Data are summarized as intake of micro- and macronutrients, food groups, and dietary patterns. ASA24 has been validated against more expensive, time-consuming tools.⁷¹ We have experience using this measure in diverse groups.^{48,49}

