Effectiveness will be assessed via our primary, secondary and patient-centered outcomes.

Adoption is a measure of potential intervention uptake by WIC. We will quantitatively assess number of provider referrals for study entry.

Implementation will be examined on both the participant level and the WIC provider level. At the participant level, we will measure intervention engagement via: 1) number of responses to self-monitoring text prompts, text response time, and the type/frequency of texted videos viewed; 2) type/frequency of FB or Instagram posts and/or likes; and 3) number/duration of WIC provider visits and calls completed. Relying on an approach by Olson and colleagues, we will examine the extent to which level of engagement is associated with gestational weight gain.⁸⁵ We will also evaluate the consistency of the intervention across different patient/provider subgroups. At the WIC provider level, we will examine process data stored in our web application and perform chart reviews to assess documentation of weight-related counseling to measure intervention delivery fidelity.

Maintenance of weight change will be assessed at 6- and 12-months postpartum. We will determine the proportion of women in each treatment group at (+/- 0.9kg) or below early pregnancy weight by 6 months and 12 months postpartum. While observational data repeatedly suggest that excessive gestational weight gain is the strongest predictor of postpartum adiposity,³ few studies have evaluated this relationship in the context of a clinical trial. With participant consent, we will additionally abstract their infant's weight and length from their pediatrician visits. These will be used to approximate measures at 6-months and 12-months of age and assess maintenance of intervention effects on infant weight/length.

iii. **Data analysis plan:**

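### The engagement analysis counts nutritionist calls without separating scheduled calls from calls triggered by weight gain, so the call–gain association can mislead in either direction (minor; cheap to repair)

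*Combined protocol and SAP*

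**What the plan says.** All references are to the combined protocol and SAP.

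- **Engagement measure (9.d.ii.5, Implementation).** There are three groups of metrics: texts and videos ("number of responses to self-monitoring text prompts, text response time, and the type/frequency of texted videos viewed"), social media activity, and "number/duration of WIC provider visits and calls completed". The analysis is then announced: "we will examine the extent to which level of engagement is associated with gestational weight gain". It is introduced with "Relying on an approach" taken from a cited paper.
- **Calls (9.c.iii.4, WIC provider counseling).** Study calls are monthly to bimonthly, with goal-assignment calls every 8 weeks. In addition, the WIC champion is "notified when a participant in this group is -0.3kg from her weekly maximum IOM recommended weight gain targets", or above them, and is "asked to call these participants within 48 hours using adapted problem solving call scripts". There is a ceiling of one call of 15-30 minutes a month.
- **Outcome (9.d.i).** Excessive gain is "defined as the proportion of mothers exceeding weekly Institute of Medicine (IOM) weight gain targets": above 0.32 kg/week for BMI 25-29.9 and above 0.27 kg/week for BMI 30 or more, from enrolment to the end of pregnancy.
- **Analysis (9.d.iii.2).** Confounders are controlled as needed, and RE-AIM outcomes are exploratory.

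Section 9.c.iii.4 leaves two things open: whether the alert is on cumulative or single-week gain, and whether the ceiling covers all calls or only alert calls. Sections 9.d.ii and 9.d.iii do not separate scheduled calls from alert calls.

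**The concern.** A woman who gains quickly is called because she gains quickly. Counting that call as engagement, and then relating engagement to gain, runs partly from outcome to exposure. Adjusting for baseline covariates does not help, because the trigger acts through the gain as it develops.

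A second force works the other way. Women who answer their calls may also be those who gain less, which makes calls look protective. Which force prevails depends on operating details that the plan does not state.

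Counselling by WIC providers is what is new relative to the pilot, which used research staff for interpersonal support (section 5). An association that points either way when calls have no effect would misinform the dissemination evaluation. The stakes stop there: the plan promises only an association, and the primary analysis compares the arms as randomised.

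**Working it through.** The plan gives no figure for the engagement analysis, so there is none to reproduce. The check simulates the intervention arm with the true effect of calls set to zero.

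**Inputs from the documents.** 40% with excessive gain and 186 women per arm (9.d.iii.4); weekly self-weighing (9.c.iii.2); alert at the limit minus 0.3 kg; goal calls every 8 weeks or calls monthly; 15-30 minutes a call; ceiling of one a month (9.c.iii.4); limit 0.27 kg/week (9.d.i).

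**Assumed.** 24 weeks of follow-up; SD of a woman's average weekly gain 0.20 kg; week-to-week SD 0.2 kg; weighing noise SD 0.5 kg; weighing compliance 90%; call completion 80% for a typical woman, varying between women (SD 1 on the logit scale). The plan's figure of more than 90% self-weighing compliance comes from earlier studies.

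**Model.**
- Average weekly gain: s = 0.27 + 0.20 × (u - 0.253), with u standard normal, so that P(s > 0.27) = P(u > 0.253) = 0.40.
- Probability of completing a call: logistic(ln(0.8/0.2) + v), with corr(u, v) = ρ. Averaged over women this is about 0.76.
- Alert in week t: measured cumulative gain ≥ 0.27t - 0.3 (cumulative reading), or measured change in the week ≥ 0.27 - 0.3 = -0.03 kg (single-week reading; 0.32 - 0.3 = 0.02 kg in the lower BMI class).
- Fitted: logit P(excessive gain) = a + b × completed calls; OR = exp(b).

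**Hand check of the reading that best fits the stated call frequency** (cumulative alert, 8-weekly goal calls, at most one call a month in all). There are 24/4 = 6 months: 3 hold a goal call and 3 are free. The simulation gives 5.8 of 6 months with an alert in women with excessive gain, against 1.8 in the others.
- Excessive gain: 3 + 3 × 5.8/6 = 5.9 calls opened; × 0.76 = 4.5 completed.
- No excessive gain: 3 + 3 × 1.8/6 = 3.9 calls opened; × 0.76 = 3.0 completed (simulated 3.1, because alerts are not spread evenly over months).
- Gap: 4.5 - 3.1 = 1.4 calls, or 1.4 × 15 = 21 to 1.4 × 30 = 42 minutes.

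**Results, no call effect, OR for excessive gain per completed call.**

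| Alert and ceiling reading | ρ = 0 | ρ = -0.3 |
|---|---|---|
| Cumulative; 8-weekly calls; ceiling on all calls | 2.1-2.2 | about 1.8 |
| Cumulative; monthly calls; ceiling on all calls | 1.00 | about 0.8 |
| Single-week alert | 1.02-1.04 | about 0.8-0.9 |
| Scheduled calls only, any reading | about 1.0 | about 0.7-0.8 |

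A second parameter set (enrolment at 10-16 weeks, 75% completion, less variation between women) gives 2.38 and 2.04 in the first row.

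**Sensitivity.** Where alert calls add to the count, 30% call completion lowers the OR to 1.2-1.6 at ρ = 0, 1.0-1.3 at ρ = -0.3 and 0.8-1.1 at ρ = -0.6. For an assumed equal-weight composite of texts, social media and calls with a cumulative alert, the OR per SD is 1.52-1.85 at ρ = 0 and 1.03-1.25 at ρ = -0.3.

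**The case against.** The other side has five fair points.

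1. **The bias is conditional.** It needs a cumulative alert, room for extra calls, and calls that enter the exposure. A reader might infer that the plan will make nutritionist calls look harmful. The documents do not support that: under other permitted readings the alert-driven bias is nil, and adherence can reverse the sign. What stands is that the sign depends on unstated details. A single-week alert would fire at 0.02 or -0.03 kg, so almost any gain would set it off. That makes the cumulative reading more workable, but the text does not settle it.
2. **Larger figures are available but fit the text less well.** If the ceiling binds alert calls only, on top of 8-weekly goal calls, the simulated counts are 6.7 against 3.7, or 45-90 minutes. That means 3 + 5.8 = 8.8 calls opened in 24 weeks, one every 24/8.8 = 2.7 weeks, which sits badly with monthly to bimonthly calls. The gap of 1.4 calls is the fairer figure; the OR is much the same (about 2.1).
3. **The cited approach may not use calls.** The reference list describes a secondary analysis of usage of an eHealth intervention, which hints at electronic metrics that weight does not trigger. This cannot be checked here. Section 9.d.ii.5 itself lists calls among the engagement measures.
4. **Confounders will be controlled.** The wording is generic, and baseline adjustment does not undo a trigger driven by the outcome.
5. **The analysis is exploratory and promises only an association.** This is correct, and it sets the severity. It does not make the association interpretable.

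**Conclusion.** The point holds as a minor one. To the extent that calls enter the engagement measure, part of the exposure is caused by the outcome, and nothing in the plan separates that part. On the reading that best fits the stated call frequency, with a cumulative alert, calls with no effect would show an OR of about 2.1-2.2 each, or about 1.8 if adherence and gain correlate at -0.3. On the other readings the alert-driven bias is close to nil, and the same correlation gives false protection. The sizes rest on the assumed variances, completion and weighing rates; poor adherence or a composite score dilutes them.

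Two stronger inferences should be resisted. The text and social media metrics are not triggered by weight, so the whole engagement analysis is not undermined. The primary result is not touched either, because women are analysed as randomised whatever their engagement.

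**What to change.** In section 9.d.ii.5, or the SAP text for it:

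- Tag each call as scheduled goal-assignment or alert-triggered, from the script used or the call records.
- Use the share of scheduled 8-week goal-assignment calls completed as the call-engagement exposure. Keep alert-triggered calls out of any engagement score.
- Count a goal call merged with an alert call as completed if goals were assigned on it. Remove from the denominator a goal call displaced by an alert call. Report how often each occurs. Scoring displaced calls as missed would itself bias the null OR (0.81, 0.60 and 0.37 at assumed displacement of 10, 25 and 50%); removing them gives 1.00-1.01. The rule is not neutral in every case: if an unreached alert call leaves a second try at the goal call, it gives 1.5-2.2. The reported frequencies therefore matter.
- Report alert calls and in-person visits (number and duration) separately, as descriptive process data.
- Adjust for BMI class and gestational age at enrolment. Describe the result as a non-causal association within the intervention arm that adherence can still confound (null OR about 0.7-0.8 for scheduled calls at an assumed correlation of -0.3).
- Reconcile section 9.c.iii.4 on whether the alert is cumulative or single-week and which calls the ceiling covers. No view is taken here on which is right.

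The cost is a few lines of SAP wording and a call-type field. The documents do not say that call type is logged. Possible sources are the process data ("we will examine process data stored in our web application"), the call scripts and the audiotapes. The downside is a coarse exposure, two or three scheduled calls per woman, and some coding work.

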- a. **Recruitment Sites:** To maximize recruitment, while WIC is conducting visits virtually, data queries and phone screening by WIC staff will include participants from all 10 of Philadelphia WIC's community clinic sites. Once sites resume in-person visits, we will resume in-person recruiting.
 - i. North Philadelphia WIC Clinic, [name]
 - ii. Olney-Logan WIC Clinic, [name]
 - iii. Aramingo WIC Clinic, [name]

- iv. South Philadelphia WIC Clinic, [name].
- v. Northeast WIC Office, [name].
- vi. Overbrook WIC Office, [name]
- vii. Woodland WIC Office, [name].
- viii. St. Christopher WIC, [name]
- ix. Lehigh WIC Office, [name]

b. Research Procedures Site:

Assessment visits (combined CORE Screening/Enrollment (CS/EN) [\leq 16 weeks gestation], end of pregnancy [36-38 weeks' gestation], 6-months postpartum, and 12-months postpartum) will occur over the phone with Temple research staff member. All staff will complete calls from a private space.

If public health guidelines allow and participants consent, these calls may be conducted as in-person visits at Temple's CORE office ([name]) or if transportation is an issue, we will conduct these visits at the participants' home.

7) Prior Approvals

WIC is strongly supportive of our efforts (see updated approval letter attached from WIC).

8) Study Design

a. Recruitment Methods: Up to 600 women will be recruited and consented for this study. We plan to enroll and randomize a total of 438 participants (219 per arm). Based on prior studies ([name] PI, Protocol #20227, "The effects of an electronically-mediated, pregnancy and postpartum, behavioral intervention program on changes in weight and cardiometabolic biomarkers: Healthy4Baby" NIH K23HL106231-01 and [name] PI, Protocol #22201, "Targeting pregnancy-related weight gain to reduce disparities in obesity: a randomized control trial" HRSA R40MC26818), we will likely need to recruit and screen approximately 40% more women than our randomization target (as we anticipate no-shows to baseline visits).

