5. Facebook and Instagram. In keeping with our strategy in prior studies, supplemental skills training materials, links to videos, and/or contests with prizes will be posted daily on an optional private Facebook (FB) group that participants will be invited to join at baseline. We chose to incorporate FB because data suggest a strong link between social influence and healthy (or risky) behaviors, particularly among young adults,⁵⁸ which we and others have leveraged through FBs unique communication features (e.g., frequent messaging/posts to increase exposure to weight-related skills; reciprocal interactions through instant messaging and/or FB “pokes” for persuasion).^{59,60} Philadelphia WIC providers actively use FB to promote local programs and communicate with current patients, and thus, we do not anticipate difficulty maintaining/moderating our group page. To ensure confidentiality, this group will be completely private, have a generic name, and will not appear on profile pages. Evidence from Healthy4Baby and Healthy Babies and other studies using social networking sites within mHealth/eHealth interventions demonstrate efficacy for their use with obesity treatment.^{18,19,61-65} Due to feedback from participants, we additionally added an optional private Instagram profile to allow participants to interact with other participants in the program and to learn new tips about staying healthy.

d. Data Analyses:

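### The exploratory engagement score partly reflects when a woman was in the programme, so its association with weight gain may be confounded by period

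*Combined protocol and SAP*

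**What the plan says.** All references are to the combined protocol and SAP.

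- **Engagement measures (9.d.ii.5, Implementation).** There are three groups: text responses and videos viewed; Facebook or Instagram activity; and "number/duration of WIC provider visits and calls completed". The plan then states that "we will examine the extent to which level of engagement is associated with gestational weight gain". No denominator, availability date or calendar covariate is given there.
- **In-person support (9.c.iii.4).** If participants agree, "they will also receive in-person support at their regularly scheduled WIC visits every 2-3 months". The next sentence reads: "While WIC is conducting visits virtually, we will not be using this approach".
- **Calls (9.c.iii.4).** "Participants will have monthly to bimonthly study-related phone calls from a WIC nutritionist". This does not depend on WIC's operating mode. Further calls are prompted when a woman's gain comes close to or exceeds her weekly maximum target.
- **Operating mode (6.a).** "Once sites resume in-person visits, we will resume in-person recruiting". The plan therefore expects more than one period.
- **Instagram (9.c.iii.5).** "Due to feedback from participants, we additionally added an optional private Instagram profile". No date is given.
- **Analysis of additional aims (9.d.iii.2).** There is a general undertaking to control confounders where needed, with no list, and RE-AIM outcomes are declared exploratory.

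**The concern.** A raw count of provider contacts treats two different situations alike: a woman who was offered in-person support and did not take it up, and a woman to whom it was never offered. The second has fewer possible contacts only because of her dates in the programme. That is a measurement weakness whatever happens to weight.

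It becomes confounding if the period is also related to measured gain. The documents describe a possible route. Weight at the enrolment call or visit may be measured or self-reported (8.c.v). Study weights come from a staff-operated clinic scale or a home scale, with the home scale used for remote participants and under Covid-19 restrictions (9.d.i). If the two periods differ in how weight was obtained, engagement and gain could be correlated with no effect of engagement. A reader of the Implementation results might then credit nutritionist visits with a difference that lies between periods.

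**Working it through.** **1. Number of women.** The plan's figure reproduces. For 55% versus 40%, two-sided 0.05 and power 0.80, the continuity-corrected formula gives 186 per arm, and 186 / 0.85 = 218.8, so 219. The engagement analysis uses the intervention arm only, so n = 186 evaluable women.

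**2. Could the cohort be split by period?** Counting back from the estimated completion in December 2023 by 18 months of participation and 30 months of enrolment (section 8.e) puts enrolment at roughly December 2019 to June 2022. The September 2021 approval falls about 21 months in. A split is possible, but no switch dates are given, so the virtual share has to be assumed.

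**3. How much of the contact count depends on availability?** From 16 weeks to 36–38 weeks is 20–22 weeks, or 4.6–5.1 months.
- In-person contacts every 2–3 months: 4.6/3 = 1.5 to 5.1/2 = 2.5.
- Routine calls every one to two months: 4.6/2 = 2.3 to 5.1.
- In-person share of contacts: (1/3)/(1/3 + 1) = 25% to (1/2)/(1/2 + 1/2) = 50% when available, and 0% when withdrawn.

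**4. Size of a possible period effect (assumed).** A systematic self-report error of 0.5 to 2 kg in baseline weight would move weekly gain by 0.5/22 = 0.02 to 2/20 = 0.10 kg/week, against the 0.27 kg/week threshold. I use 0.02 to 0.06, the lower part of that range. Whether a self-reported weight ever enters the gain calculation is unclear: 8.c.v collects it to check eligibility, and 9.b.ii says weight at each time point is taken in person or on the home scale.

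**5. False-positive rate with no true engagement effect.** Assumptions: virtual share p; V = 2.2 mean in-person visits when available and none otherwise; C = 3.7 mean calls (midpoint of 2.3 and 5.1); Poisson counts; SD of gain 0.2 kg/week; shift d higher in the virtual period.

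- Var(E) = C + (1−p)V + p(1−p)V²
- Var(Y) = 0.2² + p(1−p)d²
- r = −p(1−p)Vd / √(Var(E)·Var(Y))
- z = |r|·√(n−3), with √183 = 13.53
- rejection rate = 1 − Φ(1.96 − z) + Φ(−1.96 − z)

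For p = 0.5, Var(E) = 3.7 + 1.1 + 1.21 = 6.01. For p = 0.9, Var(E) = 3.7 + 0.22 + 0.44 = 4.36.

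| Virtual share | d (kg/week) | r | z | False positives |
|---|---|---|---|---|
| 50% | 0.02 | −0.022 | 0.30 | 6% |
| 50% | 0.04 | −0.045 | 0.60 | 9% |
| 50% | 0.06 | −0.067 | 0.90 | 15% |
| 90% | 0.02 | −0.009 | 0.13 | 5% |
| 90% | 0.04 | −0.019 | 0.26 | 6% |
| 90% | 0.06 | −0.028 | 0.38 | 7% |

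Simulations of this setting gave 13 to 15% at the top of the 50% rows and agreed with the other rows to within about a percentage point. With d = 0 the covariance is zero and the rate is the nominal 5%. Within a period, E and Y are independent in this model, so adjusting for period restores about 5% (4–6% in simulation).

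**6. Sensitivity.** If visits are half of all contacts (2.4 visits, 2.4 calls) and the shift is 0.4 SD (0.4 × 0.2 = 0.08 kg/week), the simulated rate reaches 30% at a 50% share. That is a larger shift than the range used above.

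**7. What the calculation leaves out.** It treats call counts as unrelated to gain. Section 9.c.iii.4 prompts calls on the basis of gain, so part of the call count is a consequence of the outcome. A period covariate does not touch that.

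**The case against.** The case on the other side is substantial, and most of it stands.

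- **No passage says that the period changes weight gain.** Without that link there is no bias. A reader might infer that the association is confounded; the documents support only that it may be. Weighing mode is also partly the participant's choice, and Temple's assessments are separate from WIC's operations, so the two need not move together.
- **The plan already provides for confounder control and labels RE-AIM exploratory.** This is correct. But no covariate is named, and the examples of baseline predictors in 9.d.iii.1 (age, parity, BMI, gestational age) do not include calendar period. Nor can a covariate alone separate support declined from support never offered.
- **Women in the virtual period do not necessarily score zero visits.** The measure pools visits with calls and does not restrict visits to in-person ones; WIC visits continue virtually. Only part of one measure is affected.
- **Instagram is a weak example.** A reader might infer that women enrolled earlier could not use it. The start is undated, the feedback may have come from participants in previous studies, use is optional, and it is pooled with Facebook, which it may simply have displaced.
- **Larger error rates are tempting.** Counting visits alone in all 219 women, with half in the virtual period, gives about 18% at 0.04 and 35% at 0.06 kg/week. That ignores both the calls in the planned measure and the planned 15% loss.
- **The wider RE-AIM conclusions do not rest on this.** It is one analysis within one of five dimensions, and the plan speaks of association, not effect.

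**Conclusion.** The concern holds in a limited form. The documents establish that in-person support is period-dependent, that contact counts enter the engagement measures without reference to what was offered, and that no period covariate is named. They do not establish that the period affects gain, so confounding is a possibility and not a demonstrated fault.

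Under the stated assumptions (no true effect, n = 186, 2.2 visits when available, 3.7 calls, SD 0.2, shift 0.02–0.06 kg/week), the false-positive rate is about 6–15% with half the women in the virtual period and 5–7% with 90%, against a nominal 5%. The virtual share, the shift, the SD and the contact rates are assumptions, not trial data. The randomised intention-to-treat comparison and the sample size are unaffected. This is a minor improvement to an exploratory analysis.

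**What to change.** In section 9.d.ii.5 (Implementation), or in a short SAP addition:

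1. Record the dates on which each channel was open, including the start of Instagram.
2. Score in-person support as completed relative to offered, or analyse it only among women to whom it was available. Treat Instagram the same way if it was added after enrolment began.
3. Include enrolment period (in-person or virtual WIC operation) and weight-measurement mode as covariates in every model relating engagement to weight gain.
4. Report calls triggered by weight gain separately from routine calls, because the former are partly caused by the outcome and item 3 does not correct for that.

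The cost is SAP wording, a log of dates, and a flag for call type if the call records do not already carry one. Nothing more is asked of participants and the sample size does not change. The downside is that channel-specific analyses use fewer women.
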